10.4.1 Variable

The quantities of primary interest are rates of dose limiting toxicities (DLTs) at the different dose levels, and the MTD and/or RPTD for the desired patient population.

10.4.2 Statistical hypothesis, model, and method of analysis

10.4.2.1 Dose escalation

The initial 3 cohorts will have RUXOLITINIB administered at a fixed dose of 10mg PO BID and cohort 1 will combine PANOBINOSTAT at a dose of 10mg PO TIW QOW, cohort 2 will be PANOBINOSTAT 15mg PO TIW QOW and cohort 3 will be PANOBINOSTAT 20mg PO TIW for cumulative cycle doses of 60mg, 90mg and 120mg, respectively. If an MTD of Panobinostat is not established by cohort 3, then cohort 4a will test RUXOLITINIB at 15mg PO BID in combination with PANOBINOSTAT 15mg PO TIW QOW. Cohort 4b will test RUXOLITINIB at 15mg PO BID in combination with PANOBINOSTAT 20mg PO TIW QOW. If an MTD of Panobinostat is established in the first 3 cohorts, then the cohort 4a will test RUXOLITINIB at 15mg PO BID in combination with PANOBINOSTAT at the dose level preceding the MTD dose level of PANOBINOSTAT.

If the dose escalation of Ruxolitinib continues to cohort 4b and this cohort does not define the MTD of Ruxolitinib, then cohort 5 will allow patients to be treated at a dose of PANOBINOSTAT of 10mg PO TIW QW for a cumulative dose/cycle of 120mg. Cohorts 6 and 7 will be pursued if the previous cohorts don't reach MTD and will include 15mg PO BID of RUXOLITINIB and PANOBINOSTAT at 15mg PO TIW QW and 20mg PO TIW QW, respectively.

The RPTD of each agent will be determined by the MTD and the dose limiting toxicities observed in Phase I. Subjects can start single agent ruxolitinib as long as the dose evaluation period of the previous cohort is complete before combination therapy begins. The RPTD will not necessarily be the MTD doses reached in the Phase I dose escalation part of this study. However, the RPTD will not exceed the estimated MTD dose of either drug as determined from the drugs given in combination in Phase I.

Initially, 3 subjects will be entered into a cohort with a specified dose level for each drug.

- If 2 or more of the initial subjects experience DLT, then the Maximally Tolerated Dose (MTD) of the drug being escalated has been exceeded.

- If none of the 3 subjects initially enrolled into this cohort experiences DLT, then subsequent subjects will be enrolled into the next higher dose level of the drug being escalated.
- If 1 of the initial subjects experiences DLT, then 3 additional subjects (to a total of 6 subjects) will be enrolled into the cohort.
 - If it is found that 1 of the 6 subjects in the cohort encounters DLT, then subsequent subjects will be enrolled into the next cohort.
 - If it is found that 2 or more of the 6 subjects in a cohort encounter DLT, then the MTD of the drug being escalated has been exceeded and the next lower dose level for that drug (or frequency at which the drug is administered, as in Cohorts 5, 6, and 7) will be evaluated with a maximum of 6 patients.
- The MTD for the drug being escalated will be defined as the dose level of that drug immediately below that at which 2 or more patients out of 6 experience a DLT.
- If the final cohort under consideration in the escalation of either drug in Phase I has enrolled only 3 patients and none of these 3 patients experiences a DLT, then the cohort will be expanded to 6 patients before deciding on a MTD for that drug (or frequency of drug administration).

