The RPTD of each agent will be determined by the MTD and the dose limiting toxicities observed in Phase I. The RPTD will not necessarily be the MTD doses reached in the Phase I dose escalation part of this study. However, the RPTD will not exceed the estimated MTD dose of either drug as determined from the drugs given in combination in Phase I. The decision to define the RPTD will ultimately be made by the PI and will be based on the toxicity profiles and in part any and all data on tolerability and efficacy of the combination therapy in the Phase I patients who remain on study drugs beyond the first cycle.

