6.2.7 Dose modification and dose delay

Transfusional support as clinically indicated is also permissible at the discretion of the investigators.

Dose modification rules in Phase I cycles 2-6 (Day 29 - 168) and beyond cycle 7 (Day 169+) or any time in phase II are shown in Table 6.2.3 below. These are to be followed for patients in Phase I as well as Phase II expansion and extension stages. Dose reductions (for PANOBINOSTAT) based on platelet count will be allowed and the dose of PANOBINOSTAT will not go below 5mg PO TIW QOW. See Table 6.2.1/6.2.2 for PANOBINOSTAT and RUXOLITINIB dose levels. The dose of RUXOLITINIB will not be reduced below 5mg PO BID.

Based on the expected occurrence of thrombocytopenia in this patient population with the combination of these agents, we intend to submit a request for agency feedback form to update the safety data in terms of thrombocytopenia after 10 patients have been enrolled on this study. If the safety profile with the combination of PANOBINOSTAT and RUXOLITINIB is acceptable in terms of incidence of platelet count below $20 \times 10^9/L$ and grade 3 or higher bleeding events, then we will continue the study with a threshold of $20 \times 10^9/L$ for dose holding/modification. If there is a single incidence of grade 3 or higher bleeding in association with a platelet count of $<35 \times 10^9/L$, then this threshold will be modified accordingly. This determination will be made after review by the FDA.

Table 6.2.1 RUXOLITINIB dose levels for dose modifications in Cycles 2+ (day 29+)

Dose level	RUXOLITINIB	Comment
-1	5mg PO BID	Lowest dose allowed in the study
0	10mg PO BID	Starting dose in induction phase for all patients on study
1	15mg PO BID	Starting dose for cohort 4a, 4b

Table 6.2.2 PANOBINOSTAT dose levels for dose modifications in Cycles 2+ (day 29+)

Dose level	PANOBINOSTAT	Cumulative dose (per cycle)	Comment
-1	5mg PO TIW QOW	30mg	Lowest allowable dose on the study
0	10mg PO TIW QOW	60mg	Starting dose of cohort 1
1	15mg PO TIW QOW	90mg	Starting dose for cohort 2, 4a
2	20mg PO TIW QOW	120mg	Starting dose for cohort 3, 4b
3	10mg PO TIW QW	120mg	Starting dose for cohort 5
4	15mg PO TIW QW	180mg	Starting dose for cohort 6
5	20mg PO TIW QW	240mg	Maximum dose allowed in study

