10.8 Sample size calculation

For a cohort size of 3-6 patients, and assuming that escalation happens all the way up to and including cohort 7, and all patients are evaluable, the maximum total sample size will be 58 patients. The minimum sample size will be 33, which will occur if DLT is observed in the

first 2 patients in cohort 4a. In such a case, cohort 3 would add another 3 patients to bring its total to 6. An additional 16 patients for Phase II would bring the total to $12 + 2 + 3 + 16 = 33$. If MTD and/or RPTD is achieved earlier, the sample size will be smaller. This is a Phase I study with a 3 + 3 dose-escalation scheme, first escalating Panobinostat followed by escalation of Ruxolitinib and finally an escalation of the frequency of administration of Panobinostat, as described above. In each escalation, the probabilities of escalating to the next dose after only 3 patients, and of escalating to the next dose after 3 or 6 patients, as a function of the probability of a Dose Limiting Toxicity (DLT) for a given dose, are shown in the table below [Rubinstein and Simon, 2003] :

Probability of DLT for given dose level	.05	.10	.20	.30	.40	.50	.60
Probability of continuing escalation after only 3 pts	.86	.73	.51	.34	.22	.13	.06
Probability of continuing escalation after 3 or 6 pts	.97	.91	.71	.49	.31	.17	.08

Since this is an adaptive design, it is not known exactly how many patients will be required in the trial. If all proposed doses of both drugs, as well as both proposed frequencies of administration for Panobinostat, are such that the trial does not terminate due to DLTs, it is possible that a maximum of 42 patients will be enrolled in Phase I, given the history of enrollment up through cohort 3. Since only 12 patients have been enrolled up through cohort 3, if 6 patients are required for each cohort up through cohort 7, a total of 42 patients will have contributed to Phase I. An additional 16 patients for Phase II would bring the maximum number of patients to $42 + 16 = 58$.

In the Phase II expansion study, 22 patients treated at the MTD and/or RPTD, ensuring that there is a 90% power, at an alpha level of 5%, to detect any AE with a 10% incidence rate among patients treated at the MTD and/or RPTD. However few or many patients are enrolled in Phase I, the 6 patients at the RPTD will be carried forward as the initial 6 patients in the Phase II study (Messer et al., 2010).

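### If cohort 4a passes and 4b fails, labelling 4b a ruxolitinib step makes the per-drug rule set the ruxolitinib MTD at 10 mg, which excludes the passing 4a regimen

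*Combined protocol and SAP*

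**What the plan says.** The point concerns the branch in which no panobinostat MTD is found by cohort 3. Cohort 4a is then ruxolitinib 15 mg BID with panobinostat 15 mg TIW QOW, and 4b is ruxolitinib 15 mg BID with panobinostat 20 mg TIW QOW (6.2.3, 10.4.2.1, Table 6-2).

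- **MTD rule (10.4.2.1).** "The MTD for the drug being escalated will be defined as the dose level of that drug immediately below" the one with two or more DLTs among six patients. The step-down after a failed cohort likewise goes to the next lower level of whichever drug is under escalation, with at most 6 patients evaluated there.
- **Label for 4b (10.4.2.1, and the same in 6.2.3).** The condition for moving on to cohort 5 begins "If the dose escalation of Ruxolitinib continues to cohort 4b and this cohort does not define the MTD of Ruxolitinib".
- **Order of stages (10.8).** "first escalating Panobinostat followed by escalation of Ruxolitinib and finally an escalation of the frequency of administration of Panobinostat". There is no second panobinostat dose stage.
- **Dose tables (6.2.7).** Ruxolitinib 15 mg BID is "Starting dose for cohort 4a, 4b". Panobinostat 15 mg QOW is "Starting dose for cohort 2, 4a", and 20 mg QOW is "Starting dose for cohort 3, 4b".
- **Moving up after 0 of 3 DLTs (10.4.2.1).** "subsequent subjects will be enrolled into the next higher dose level of the drug being escalated".
- **Cap (6.2.3, repeated in 10.4.2.1).** "the RPTD will not exceed the estimated MTD dose of either drug as determined from the drugs given in combination in Phase I".

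**The concern.** The MTD and step-down rules work only if the escalated drug can be identified. At 4b the label says ruxolitinib, while the doses say panobinostat. Section 4.1 adds to the mismatch: it describes the ruxolitinib stage as one in which panobinostat is held fixed, and the step from 4a to 4b does the reverse.

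If 4b fails after 4a has passed, the label decides which regimen is the MTD, which cohort is topped up to six, and which six patients start the 22-patient phase II set. Through the cap, it can also remove from consideration a regimen that met the 3+3 criterion. Section 10.8 reports 12 patients enrolled through cohort 3, so 4a and 4b are the next cohorts to be decided.

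**Working it through.** **1. Reproducing the plan's figures (10.8).** The chance of escalating past a cohort with true DLT rate p is E(p) = (1−p)³ + 3p(1−p)² × (1−p)³.

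| p | E(p) | Table in 10.8 |
|---|---|---|
| .10 | .906 | .91 |
| .20 | .709 | .71 |
| .30 | .494 | .49 |
| .40 | .309 | .31 |

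Minimum enrolment is 12 + 2 + 3 + 16 = 33. The maximum is 12 + 5 × 6 + 16 = 58. Both agree with the plan.

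**2. Tracing the rule when 4a passes and 4b has two or more DLTs.**

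| | Escalated drug: ruxolitinib (the plan's label) | Escalated drug: panobinostat (the dose that changes) |
|---|---|---|
| Failing level | 15 mg BID | 20 mg QOW |
| MTD of that drug | 10 mg BID | 15 mg QOW |
| Step-down, other drug kept at its 4b dose | 10 mg BID + 20 mg QOW = cohort 3 | 15 mg BID + 15 mg QOW = 4a |
| Effect of the cap | ruxolitinib above 10 mg barred, so 4a is out | panobinostat above 15 mg QOW barred, so cohort 3 is out |

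The 0-of-3 bullet supports the second column. Ruxolitinib has no level above 15 mg, so a clean 4a leads to 4b only if panobinostat is the drug meant. No sentence names panobinostat as the drug escalated at 4b.

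**3. Difference between the two regimens.** Ruxolitinib is 2 × 10 = 20 mg/day in cohort 3 and 2 × 15 = 30 mg/day in 4a, so cohort 3 is one third lower. Panobinostat, at six doses per QOW cycle, is 20 × 6 = 120 mg in cohort 3 and 15 × 6 = 90 mg in 4a, so cohort 3 is one third higher.

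**4. Is the path plausible?** The plan gives no DLT rates for 4a or 4b, so the rates here are assumptions. P(4a passes and 4b fails) = E(p4a) × [1 − E(p4b)].

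- 10% and 20%: .906 × .291 = .264
- 20% and 30%: .709 × .506 = .358
- 20% and 40%: .709 × .691 = .489

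**5. Enrolment on this path.** These totals assume that the cohort named ends as the MTD.

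- Step-down to cohort 3: 12 + (3 or 6 in 4a) + (2 to 6 in 4b) + 3 + 16 = 36 to 43.
- Step-down to 4a: 12 + 6 + (2 to 6 in 4b) + 16 = 36 to 40.

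**6. If 4a is preferred, how often would cohort 3 still be needed?** This requires that 4a passed at 0 of 3 and then has two or more DLTs in its three top-up patients.

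- 4a rate 10%: share of passes at 0 of 3 is .729/.906 = .805. Top-up failure is 3(.1)²(.9) + (.1)³ = .028. Product .023.
- 4a rate 20%: .512/.709 = .723. Top-up failure is 3(.2)²(.8) + (.2)³ = .104. Product .075.

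**The case against.** The best reply is that this is loose labelling with an evident answer.

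- The bullet for 1 of 6 DLTs moves to the next cohort and does not mention a drug. Table 6-2 places 4a directly before 4b, so an ordinary 3+3 steps back to 4a.
- Section 6.2.3.1 defines the MTD as the highest dosage with DLTs in no more than 33% of patients. Read by regimen, ruxolitinib 15 mg met that standard in 4a, and the cap itself refers to MTDs found in combination.
- The only worked step-down, in 10.8, sends a failed 4a to cohort 3. Lowering ruxolitinib while keeping panobinostat at 15 mg would have given cohort 2, so the plan does not strictly hold the partner dose.
- Section 6.2.4 lets the investigators expand a cohort, add an intermediate dose or stop escalation, and the PI chooses the RPTD.

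Much of this stands. Stepping back to 4a is the more natural reading, and a sensible team might well take it. A reader might infer that the rules contradict each other outright, or that the plan compels a return to cohort 3. The documents do not go that far, because the cohort order and the MTD definition read by regimen both point to 4a.

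What remains is that none of these provisions displaces the per-drug rule or the cap. Section 6.2.3.1 is worded per drug dosage, and cohort 3 and 4a are not ordered against each other. The 10.8 example fits a return to the preceding cohort, but it fits equally well a return of ruxolitinib to 10 mg with the highest panobinostat dose that passed. Section 6.2.4 does not say what the MTD is, and the PI's discretion operates below the cap. Figure 4-2 is not shown in the available text; section 4.1 describes it as the standard 3+3 rules.

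**Conclusion.** The point holds as a mislabelled decision rule. It should be corrected before 4a and 4b are decided. Applied literally with the plan's own label, the rule sets the ruxolitinib MTD at 10 mg after 15 mg has passed in 4a, and the cap then shuts 4a out of phase II. This is limited to the branch with no panobinostat MTD by cohort 3, 4a passing and 4b failing. Confidence is moderate, because the panobinostat reading comes from the doses and the 0-of-3 bullet and is not stated outright.

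Three stronger inferences are not supported:

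- **A safety hazard.** Cohort 3 and 4a have each passed before 4b opens, and either is to be brought to six patients. Neither reading sends anyone to a failed dose.
- **A 26% to 49% chance of a wrong MTD.** Those figures are the chance of reaching this path under assumed DLT rates. They show that the path is plausible and say nothing about which choice would be made on it.
- **A faulty sample size.** Totals of 36 to 43 lie inside 33 to 58, and the escalation table and the expansion size of 22 are unaffected.

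**What to change.** In 6.2.3 and 10.4.2.1:

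1. Describe 4b as a panobinostat step at fixed ruxolitinib 15 mg BID.
2. Define the MTD, and the RPTD cap in both sections, by tested regimen: ruxolitinib dose, panobinostat dose and schedule together.
3. Add the missing sequence. If 4b has two or more DLTs, 4a is topped up to six patients if it has only three, and is the MTD with at most 1 of 6 DLTs. Otherwise cohort 3 is topped up to six and is the MTD with at most 1 of 6.

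The cost is a few lines of wording and no new procedures. Under this rule a trial in which 4b fails ends at 36 to 43 patients if 4a or cohort 3 is the MTD. The cohort 3 fallback would be needed in about 2% to 8% of cases where 4a passed and 4b failed, for assumed 4a DLT rates of 10% to 20%. The one substantive commitment is a stated preference for 4a over cohort 3, made before the 4b data are seen. The PI remains free to choose a lower RPTD.

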10.4.2.2 Dose expansion

The cohort of 6 patients at the MTD and/or RPTD will be expanded by an additional 16 patients in order to further assess safety and tolerability. Thus the number of patients treated at the MTD and/or RPTD will be 22, which ensures that there is a 90% chance to detect any AE with a 10% incidence rate among patients treated at the MTD and/or RPTD. During this phase of the study, further defining of the biological activity of this combination will be explored. The primary endpoint of this portion of the trial is response rate by IWG-MRT criteria. We hypothesize a response rate of >40% in treated patients at C6D28 will constitute a positive primary endpoint. A positive response by IWG-MRT criteria includes SD, CI, PR, or CR. Since preclinical studies suggest a synergistic effect of the two agents in combination, we would expect a spleen response rate (>35% reduction in spleen volume by MRI or >50% reduction in palpable spleen) of >30% as was assumed in the COMFORT study. Since the proportion of patients obtaining this efficacy endpoint was 42%, we will have a target response for this secondary endpoint of >50%, and this will be reported in a descriptive manner.

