	
 i. Progressive splenomegaly that is defined by the appearance of a previously absent splenomegaly that is palpable at greater than 5 cm below the left costal margin or a minimum 100% increase in palpable distance for baseline splenomegaly of 5-10 cm or a minimum 50% increase in palpable distance for baseline splenomegaly of greater than 10 cm. ii. Leukemic transformation confirmed by a bone marrow blast count of at least 20%. iii. An increase in peripheral blood blast percentage of at least 20% that lasts for at least 8 weeks.
5. Stable disease (SD)	None of the above.
6. Relapse	Loss of CR, PR, or CI. In other words, a patient with CR or PR is considered to have undergone relapse when he or she no longer fulfills the criteria for even CI. However, changes from either CR to PR or CR/PR to CI should be documented and reported.

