5.2 Inclusion criteria

- 1 Male or female patients aged \geq 18 years old
- 2 Ability to provide written informed consent obtained prior to participation in the study and any related procedures being performed
- 3 Intermediate-2 and higher by IWG-MRT Post PV/ET MF and PMF patients either in
 - a. Chronic Phase (MF-CP)
 - b. Accelerated Phase (MF-AP)
- 4 Patients must meet the following laboratory criteria:
 - a. ANC \geq $.750 \times 10^9/L$
 - b. Platelets $\geq 75 \times 10^9/L$
 - c. Creatinine $\leq 1.5 \times$ ULN,
 - d. AST and ALT $\leq 2.5 \times$ ULN
 - e. Serum bilirubin $\leq 1.5 \times$ ULN (unless Gilbert's syndrome and evidence of hemolysis)
 - f. Serum potassium \geq LLN
 - g. Total serum calcium [corrected for serum albumin] or ionized calcium \geq LLN,
 - h. Serum magnesium \geq LLN
 - i. Serum phosphorus \geq LLN
 - j. Free T4 within normal limits
- 5 ECOG Performance Status of ≤ 3
- 6 Any prior therapy with JAK2-TKI, hypomethylating agents, HDACI, mTORi, or iMiDs is allowed as long as it is greater than 3 weeks since last dose of administration and in the case of a JAK2-TKI or HDACI that discontinuation was not due to non-hematologic drug toxicity. An exception to this criteria are patients currently on at least 10mg BID of ruxolitinib for greater than 3 months and who have not shown an optimal response (i.e. without 50% reduction in palpable splenomegaly or 50% reduction in symptom burden). With a reduction of ruxolitinib to 10mg BID these patients may enter onto the study without stopping ruxolitinib.

Exclusion criteria

1. Patients who will need valproic acid for any medical condition during the study or within 5 days prior to first PANOBINOSTAT treatment.
2. Impaired cardiac function or clinically significant cardiac diseases, including any one of the following:
 - a. With permanent cardiac pacemaker

- b. Resting bradycardia defined as <50 beats per minute
- c. QTcF >480 msec on screening ECG
- d. Complete Left bundle branch block, bifascicular block
- e. Any clinically significant ST segment and/or T-wave abnormalities
- f. Presence of unstable atrial fibrillation (ventricular response rate >100 bpm).
Patients with stable atrial fibrillation can be enrolled provided they do not meet other cardiac exclusion criteria.
- g. Symptomatic congestive heart failure (NYHA class III-IV)

3. Impairment of GI function or GI disease that may significantly alter the absorption of PANOBINOSTAT or RUXOLITINIB

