10.4 Primary objective

The primary objective of the phase I trial is to establish safety and tolerability of the combination of PANOBINOSTAT and RUXOLITINIB as well as the MTD and/or RPTD in patients with MF. The primary objective of phase II is to determine the proportion of patients that achieve at least SD by IWG-MRT treatment response. The target IWG-MRT treatment response rate of >40% in the phase II part of this study will signify a positive result.

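### The Phase II success rule counts stable disease, a residual category, as response: nine stable patients of 22 with no objective response would be declared positive

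*Combined protocol and SAP*

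**What the plan says.** **Endpoint and bar.** Section 10.4 of the combined protocol and SAP states: "The primary objective of phase II is to determine the proportion of patients that achieve at least SD by IWG-MRT treatment response". It adds that a rate above 40% will signify a positive result. Section 10.4.2.2 repeats the bar, "We hypothesize a response rate of >40% in treated patients at C6D28 will constitute a positive primary endpoint", and lists what counts: "A positive response by IWG-MRT criteria includes SD, CI, PR, or CR". The sample is given there as well: "Thus the number of patients treated at the MTD and/or RPTD will be 22", made up of six patients from Phase I and 16 more.

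**Categories.** Table 4-1 (Section 4.1) defines SD as "None of the above". Its spleen criterion for progressive disease (PD) is measured against baseline, for example "a minimum 50% increase in palpable distance for baseline splenomegaly of greater than 10 cm".

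**Progression elsewhere.** Section 7.2.1 documents progression by a spleen length more than 25% above the on-study nadir, or by the investigator's judgment of symptoms or of a rise in blasts. Section 7.1.5.1 requires patients who progress to be discontinued.

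**Denominator and missing data.** Section 10.4.2.2 speaks of treated patients and of 22 treated at the recommended Phase II dose (RPTD). Section 10.1.1 makes everyone with at least one dose of study medication the primary efficacy set, and Section 6.1 counts ruxolitinib as study drug. Section 10.4.3 covers only replacement and continuing events. Section 7.1.5.2 says withdrawn patients are not replaced, apart from a Phase I evaluability exception.

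**The concern.** A residual category needs no change in the patient. Section 5.2 also admits, without stopping the drug, "patients currently on at least 10mg BID of ruxolitinib for greater than 3 months and who have not shown an optimal response", subject to a reduction to 10 mg BID. Such a patient already taking 10 mg BID who stays as they were through Cycle 6 is SD, and so counts as a response. The endpoint is therefore mainly a measure of non-progression, yet the plan calls it treatment response and sets a pass mark whose origin is not given.

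Two things are at stake. A positive primary result could be reported as response when no patient met CI, PR or CR. And with 22 patients the result can turn on scoring decisions that the plan leaves open: what happens to a treated patient who has no Cycle 6 assessment, and which progression definition separates SD from PD.

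**Working it through.** **1. The plan's own figure.** The only numerical basis for 22 patients is detection of an adverse event with 10% incidence: 1 − 0.9^22 = 0.9015, which reproduces the stated 90%. It says nothing about response. No null rate, alternative or test is given for the 40% bar, so there is no stated operating characteristic to reproduce.

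**2. Pass mark.** 0.40 × 22 = 8.8, so the smallest passing count is 9: 9/22 = 40.9%, while 8/22 = 36.4% fails.

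**3. Exact (Clopper-Pearson) 95% intervals.**
- 9/22: 20.7% to 63.6%.
- 0/22: upper limit 1 − 0.025^(1/22) = 15.4%.

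Nine SD and no CI, PR or CR meets the rule with an objective response rate of 0%.

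**4. Chance of passing**, P(X ≥ 9) for X binomial with n = 22:

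| True SD-or-better rate | P(rule met) |
|---|---|
| 30% | 0.187 |
| 40% | 0.546 |
| 50% | 0.857 |
| 60% | 0.979 |

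**5. Unassessed patients.** An unassessed patient can be read as not having achieved SD, or as falling into the residual category. Assumed examples, all with 22 treated:
- 7 SD, 5 unassessed, 10 PD: 7/22 = 31.8% fails; (7 + 5)/22 = 54.5% passes.
- 8 SD, 1 unassessed, 13 PD: 8/22 = 36.4% fails; 9/22 = 40.9% passes.

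**6. Induction-only patients.** Section 4.1 gives ruxolitinib alone for 28 days and adds panobinostat only if the Day 1 platelet condition is met. A patient who stops there belongs to the Section 10.1.1 set but was not treated with the combination at the RPTD, as Section 10.4.2.2 describes the 22.

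**7. Two progression definitions.** Take a spleen of 12 cm at baseline, 8 cm at nadir and 11 cm now.
- Section 7.2.1: 11/8 − 1 = 37.5%, above 25%, so progressed.
- Table 4-1: spleen PD needs 12 × 1.5 = 18 cm, so not PD. The best reduction was 1 − 8/12 = 33%, short of the 50% needed for CI. With no other criterion met, the patient is SD and counts as a response.

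**The case against.** The best defence is that counting SD is explicit, prespecified and consistent with the rule that patients with at least SD may continue (Sections 4.1 and 7.1.4.2). Disease control is a legitimate endpoint. Spleen, marrow and transfusion outcomes are planned in Sections 10.6.1 to 10.6.5, so a result made only of SD would be visible. This stands as a reason to keep the rate. It does not justify calling the rate response, or an unexplained bar.

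It can also be said that Section 10.4 asks who achieves at least SD, so an unassessed patient has naturally not achieved it, and that the endpoint is scored by IWG-MRT, hence by Table 4-1, with Section 7.2.1 serving withdrawal. Both are the likelier readings, but neither is written down. A patient withdrawn under Section 7.2.1 before Cycle 6 also becomes an unassessed patient.

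Some stronger readings are tempting but not supported:
- *A positive result shows at most non-progression.* That is the minimum it guarantees; the responders could include many with CI, PR or CR.
- *Unassessed patients might be dropped*, turning 8/22 into 8/19 = 42.1%. Sections 10.1.1 and 10.4.2.2 both keep treated patients in the denominator.
- *One induction-only patient turns 9/22 into 9/23 = 39.1%.* In the expansion part Section 10.4.3 does not replace a patient who is in the safety set. The comparison is then 9/22 with 9/21 = 42.9%, both positive.
- *The bar is incoherent because the narrower spleen endpoint has a higher one* ("we will have a target response for this secondary endpoint of >50%, and this will be reported in a descriptive manner"). Section 10.6.2 ties that target to Week 12 or end of study, so the two endpoints are not strictly nested.
- *Section 7.2.2.1 contradicts the endpoint* by calling patients below a 50% spleen reduction IWG-MRT non-responders. It sits under splenic palpation and probably means spleen response only.
- *Panobinostat alone already reached 50%* (4 CI + 5 SD of 18, Section 1.2.3). Eight of those 18 have no reported category and the regimen differs, so it is not a benchmark.

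**Conclusion.** The concern holds. As written, Phase II is positive at 9/22 with at least SD, and this can happen with 0/22 objective responses (exact 95% upper limit 15.4%). The rule passes with probability 0.55 if the true SD-or-better rate is 40% and 0.86 if it is 50%. A positive result does not by itself show objective response.

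Three scoring points are also open: the treated patient without a Cycle 6 assessment, the induction-only patient, and the boundary between SD and PD. The first can decide the result. The second is an inconsistency between sections, and one such patient does not change the outcome at the pass mark. The third can move individual patients across the boundary.

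These figures assume 22 patients in the denominator, independent outcomes, and the 40% bar read as a rule on the observed proportion, as Section 10.4 words it. The missing-data and spleen examples are illustrations, not forecasts.

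**What to change.** Keep 22 patients, the C6D28 time point and SD-or-better above 40% as the stated primary rate. In Sections 10.4 and 10.4.2.2:

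1. Label the rate disease control (non-progression). State the benchmark behind 40%, or call the bar descriptive. Add that exceeding it will not by itself be taken to show treatment response.
2. Report CR+PR+CI per Table 4-1 beside it, both with the exact 95% interval already used in Section 10.6.2.
3. Define the denominator as all patients who started the combination at the RPTD. Count those without a Cycle 6 IWG-MRT assessment as not achieving SD or better. List induction-only patients separately, and reconcile this with Section 10.1.1.
4. State that Table 4-1 scores the endpoint, reconcile Section 7.2.1 with it, and limit the wording of Section 7.2.2.1 to spleen response. The withdrawal rule itself is a clinical matter for the sponsor.

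**Cost.** No new data are needed, but Section 12.1 requires a written, IRB-approved amendment. It should record which responses were already known, because Section 10.8 reports 12 patients enrolled through cohort 3 and carries six open-label Phase I patients into the 22. The headline becomes less favourable. CR+PR+CI may understate activity in patients with no route to CI: entry does not require splenomegaly, and the platelet minimum of 75 × 10^9/L at entry is above the level from which the platelet route applies. That is why it is reported beside the primary rate and does not replace it.
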